1.3 CLINICAL STUDIES

To date, the development program of ESN364 includes only one recently completed study, conducted in 65 subjects. A dose range between 3 and 180 mg as single dose in fasted and fed conditions, and up to 21 days of dosing in a multiple dose setting was tested. Both sexes were included in this study. Male healthy volunteers have been dosed up to 10 consecutive days and healthy female subjects of childbearing potential have been dosed up to 21 consecutive days in accordance with their menstrual cycle. The highest dose in both multiple dose parts was 180 mg q.d.

The results of the Phase I study demonstrated that administration of single and multiple ascending doses up to 180 mg of ESN364 were safe and well tolerated.

No deaths occurred during the study. The majority of reported treatment-emergent adverse events (TEAEs) were mild to moderate in severity. A severe TEAE was reported in 1 (7.1%) subject in the placebo treatment group. One serious adverse event (SAE) (foot fracture) was reported in 1 (5.9%) subject during the follow-up period and led to withdrawal of the subject from the study.

The most frequently reported TEAEs (i.e., those reported in >2 subjects per treatment group) following multiple ascending dosing for 21 days in healthy female subjects were abdominal pain in 3 (50.0%) subjects each in the placebo and 180 mg ESN364 treatment group, nausea in 3 (50.0%) subjects in the 20 mg ESN364 treatment group, headache in 3 (50.0%) and 4 (66.7%) subjects in the 60 mg and 180 mg ESN364 treatment groups,

respectively, and dry skin in 3 (50.0%) subjects in the 180 mg ESN364 treatment group. Nausea and headache were only reported in the 20 mg, 60 mg, and 180 mg ESN364 treatment groups and not in the placebo treatment group.

All subjects had recovered or were recovering from the TEAEs by the end of the study.

All treatment-emergent laboratory abnormalities (worst-case) were observed in at most 2 subjects per treatment group, except for some isolated elevated abnormally high potassium levels and isolated low levels of total bilirubin. None of the laboratory abnormalities were considered to be of clinical relevance, and as a consequence none of the laboratory abnormalities were reported as adverse event (AE).

No clinically relevant trends or changes were observed in median vital sign values and ECG parameters over time. None of the observed ECG related abnormalities were reported as AE. Vital sign abnormalities were reported as a AE in 2 subjects (palpitations in one subject after single dose administration and palpitations and orthostatic hypertension in one subject after multiple dose administration).

None of the subjects were observed with new (i.e., not present at screening) abnormal findings during physical examination in the study.

In female subjects, a dose-dependent decrease in detectable ovulations and a delay of the mid-cycle LH surges was observed, resulting in a prolonged or absent menstrual cycle. A 84-day follow-up period showed a recovery of the normal menstrual pattern once the treatment with ESN364 had finished.

Following single ascending dose administration of ESN364, the PK of ESN364 was dose proportional in terms of maximum plasma concentration (C_{max}) and plasma exposure (AUC_{∞}) over the 3 to 180 mg dose range. Median time to maximum plasma concentration (t_{max}) ranged between 1.25 to 2.00 hours, being longer in the 90 mg dose group compared to the 3 and 12 mg dose groups. Mean terminal half-life ranged between 2.39 and 4.19 hours. No significant food effect was observed on ESN364 exposure and absorption rate measured in the 23 mg dose group.

Single dose administration of ESN364 in the dose range from 3 to 180 mg induced a dose-dependent decrease in total and free testosterone, FSH and LH plasma concentrations within the 24 hours after administration, compared to placebo. Both minimum concentration (i.e., maximum effect) and plasma exposure were decreased after different single doses of ESN364. No clear effect on sex hormone-binding globulin (SHBG) plasma concentration was observed compared to placebo.

Following multiple dose administration for 10 days in healthy males, it could be concluded that steady-state in ESN364 plasma concentrations was reached quickly, by Day 2, so after the first administration of study drug. The mean total amounts of ESN364 excreted unchanged in urine over the 0-24 hour period were similar on Day 1 and Day 10 (with a range of 1.53 to 2.16% of the dose). The bioavailability of ESN364 increased proportionally with the dose from 20 to 180 mg q.d, as measured by peak and plasma exposure. Time to peak concentration was similar after single and multiple administrations and for all tested doses, with median t_{max} of 2.50 or 3.00 hours. From descriptive data, the apparent elimination half-life seems to be comparable between the studied dose groups as well between single dosing and steady-state with mean values ranging between 2.84 and 4.20 hours. No accumulation of ESN364 was observed after

10 days of 60 or 180 mg q.d. administration. Renal clearance seems to be similar in the 60 or 180 mg q.d. groups, with mean values of 11 and 9.93 mL/min, respectively.

Single and multiple administration of ESN364, in the dose range from 20 to 180 mg q.d., induced a similar dose-dependent decrease in total and free testosterone within the 24 hours after administration, compared to placebo. A decrease of a similar extent throughout the dose range (20 mg to 180 mg q.d.) was observed in LH and FSH plasma concentrations after single and multiple administration of ESN364, compared to placebo. After a single administration of ESN364 (Day 1), total testosterone plasma concentrations <5.2 nmol/L were found for 16.7% of the subjects at the dose of 20 mg q.d. (for a median extent of time of 5.58 hours), for 66.7% of the subjects at a dose of 60 mg q.d. (for a median extent of time of 6.52 hours) and for 66.7% of the subjects at a dose of 180 mg q.d. (for a median extent of time of 11.5 hours). After multiple administration (Day 10) of ESN364 (Day 10), total testosterone plasma concentrations <5.2 nmol/L were found for 50% of the subjects at the dose of 20 mg q.d. (for a median extent of time of 1.77 hours), for 50% of the subjects at a dose of 60 mg q.d. (for a median extent of time of 4.21 hours) and for 66.7% of the subjects at a dose of 180 mg q.d. (for a median extent of time of 7.5 hours). After single and multiple dose administration of ESN364, no clear effect on plasma SHBG concentrations was observed, compared to placebo. Relatively high between-subject variability was observed for pharmacodynamic (PD) parameters.

Following multiple dose administration for 21 days in healthy females, it could be concluded that steady-state in ESN364 plasma concentrations was reached quickly, by Day 2, so after the first administration of study drug. The bioavailability of ESN364 increased dose proportionally between 20 and 60 mg q.d. but was above the dose proportionality for the highest 180 mg q.d. compared to 60 mg q.d., as measured by peak and plasma exposure, and this independently from PK sampling day (Day 1 and Day 21). No significant dose and day effects were observed on t_{max} with median t_{max} of 3.00 to 4.00 hours. Plasma ESN364 exposure was higher at steady-state (Day 21) compared to Day 1. From descriptive data, the apparent elimination half-life seems to be comparable between the studied dose groups as well between single dosing and steady-state (mean half-life ranged between 4.22 and 4.84 hours), with the exception of the highest dose group where the half-life was prolonged on Day 1 (7.06 hours) and Day 21 (6.34 hours) compared to the other dose groups. No relevant accumulation of ESN364 was observed after 21 days of administration of 60 or 180 mg q.d. administration, with mean accumulation ratio (R_{ac}) values of 1.23 and 1.18, respectively. Renal clearance seems to be comparable in the 60 or 180 mg q.d. groups, with mean values of 6.83 and 5.34 mL/min, respectively. When comparing ESN364 exposure after single dosing or at steady-state following multiple dose administration for 10 days (healthy males) and 21 days (healthy women), peak and plasma exposures were significantly lower in males. Time to peak exposure was similar for both genders.

Based on plasma concentrations monitored from the first administration (Day 1) to 24 hours after the last administration (Day 22) (i.e., over the time extent of the menstrual cycle during presence of study drug in the body), the time to reach the peak concentration in LH was lengthened with the 60 and 180 mg q.d. dosages (median time of \approx 17 days) compared to placebo (median time of \approx 8 days). No clear difference between active treatments and placebo could be evidenced in FSH plasma concentrations. The time to reach the peak concentration in total and free estradiol was lengthened with the 60 and

180 mg q.d. dosages (median time of between 17 and 19 days) compared to placebo (median time of \approx 9 days). A dose-dependent decrease in P4 plasma concentration was observed with the 60 and 180 mg q.d. dosages, compared to placebo, and the 20 mg q.d. dosage; the calculated median time to reach P4 peak concentration was between around 18 days for the 60 and 180 mg q.d. dosages, compared to 14 days for placebo and the 20 mg q.d. dosage. However, for a majority of subjects in the 60 and 180 mg q.d. dose groups, the menstrual peak in P4 was not yet reached at Day 22.

1.4 OVERALL RATIONALE FOR THE STUDY

Since 2012, there is an increasing number of articles and papers pointing towards a direct link between kisspeptin/neurokinin B/dynorphin (KNDy) neurons and the occurrence of hot flashes [15,16,17]. Mittelman-Smith and Rance linked the modulation of body temperature, estradiol and KNDy neurons to the occurrence of hot flashes [15,16]. Jayasena et al. demonstrated a direct causal relationship between the injection of NKB and the occurrence of hot flashes in the study participants [17].

Euroscreen did an experiment in 10 ovariectomized ewe (non-GLP study Monash 001) where the ewes were injected with either 1 mg/kg ESN364 or placebo. The study was used to demonstrate the suppression of the LH pulse frequency by ESN364. When analyzing the safety data from the ewes, there was a significant difference in core body temperature between the treated versus the placebo ewes, as shown in Figure 3.

[figure not shown]

Figure 3: Core Body Temperature in Ovariectomized Ewes Injected With 1 mg/kg ESN364 or Placebo

Our current hypothesis is that in menopause, the lack of E2 feedback to the KNDy neuron leads to an increased firing frequency of that neuron which in turn leads to the increase in plasma LH and FSH concentrations typically seen in postmenopause.

Because of the projecting nerve endings from the KNDy neuron to the preoptic hypothalamus, this increased firing of the KNDy neuron also results in the generation of hot flashes. Our hypothesis is that ESN364 - via NK3 antagonism - will decrease this firing frequency of the KNDy neuron to normal 'premenopausal' levels thus eliminating the occurrence of hot flashes.

A schematic diagram showing the anatomic relationship between KNDy neurons, GnRH neurons, and the heat-defense pathway in the rat is shown in Figure 4.

[figure not shown]

Figure 4: Schematic Diagram Showing the Relationship Between KNDy Neurons, GnRH Neurons and the Heat-Defense Pathway in the Rat. KNDy Neurons Branch and Project to GnRH Terminals in the Median Eminence and Preoptic Structures That Regulate Body Temperature (Figure from [18])

1.5 RISK BENEFIT ANALYSIS

ESN364 is being developed for the treatment of women's health disorders such as endometriosis, polycystic ovarian syndrome, and uterine fibroids. The compound may also be developed for sex hormone disorders affecting men, such as BPH.

Due to recent advances in science, there are reasons to believe that ESN364 can be an effective treatment for the symptoms and morbidity associated with menopause.

A key feature of NK3 antagonism is the selective decrease of LH secretion without compromising FSH secretion by decreasing the firing rate of the KNDy neuron.

When given to normally cycling healthy women, ESN364 is capable of altering the menstrual cycle and decreasing the circulating levels of E2, LH, P4 and testosterone. Since in this study we are aiming at including postmenopausal volunteers, these effects will become of less importance because of the physiological changes that happen in the climacterium (anovulation with loss of P4 and E2 production, and consequently increase of LH/FSH).

In terms of hormonal changes we do anticipate a moderate decrease of the already elevated LH and FSH plasma levels, maybe even to premenopausal levels. There are no known risks associated with this quasi normalization of the gonadotropins.

Treatment with ESN364 can cause adverse effects or other symptoms. Adverse effects that can be expected as derived from the AE profile of the first-in-human study in male and female healthy volunteers (see also Section 1.3) are as follows:

During the Phase I study, following side effects have been recorded in the 41 male healthy volunteers who received ESN364:

- Very Frequent (i.e., in more than 1/10 participants): none;
- Frequent (i.e., in more than 1 in 100 but fewer than 1 in 10 participants): nausea and headache (both in 3/41 participants) and palpitations, abdominal discomfort, diarrhea, oral paresthesia (tingling sensation in the mouth), dizziness,

hyperhidrosis (increased sweating), abnormal skin odor, irritability, and fatigue (each in 1/41 participants).

During the Phase I study, following side effects have been recorded in the 18 female healthy volunteers who received ESN364:

- Very Frequent (i.e., in more than 1/10 participants): headache (7/18 participants), dry skin (3/18 participants), abdominal pain, metrorrhagia, vaginal discharge, and acne (each in 2/18 participants);
- Frequent (i.e., in more than 1/100 but fewer than 1/10 participants): dry mouth, dysphagia (pain during swallowing), nausea, sensation of pressure, dizziness, breast pain, vulvovaginal itching, oropharyngeal pain, generalized itchy feeling, abnormal skin odor, palpitations, dry eye, abdominal discomfort, and abdominal distension (all in 1/18 participants).

All recorded treatment-related AEs were mild to moderate in severity and had a short duration. All AEs resolved spontaneously without sequelae. Only 3 AEs were rated moderate in severity, being abdominal pain, headache and palpitations. The reported palpitations were short-lived and were not accompanied by other signs/symptoms of cardiac involvement (vital signs and ECG were normal).

However, given the stage of drug development, our current knowledge of the side effect profile of ESN364 is still limited.

2. STUDY OBJECTIVES

2.1 PRIMARY OBJECTIVE

The primary objective of the study is to evaluate the effect of ESN364 on the severity and frequency of hot flashes in early postmenopausal women suffering from hot flashes, in terms of changes in weekly Hot Flash Score from baseline to Week 12.

2.2 SECONDARY OBJECTIVES

Secondary objectives are to evaluate in early postmenopausal women suffering from hot flashes:

- the effect of ESN364 on the severity and frequency of hot flashes, in terms of changes in weekly Hot Flash Score from baseline to Weeks 4 and 8, and at follow-up;
- the effect of ESN364 on the frequency of hot flashes, in terms of changes in weekly Hot Flash Frequency from baseline to Weeks 4, 8, and 12, and at follow-up;
- the effect of 12-week administration of ESN364 on hot flash interference on daily life, in terms of changes from baseline over time in Hot Flash Related Daily Interference Scale (HFRDIS);
- the effect of 12-week administration of ESN364 on climacteric symptoms, in terms of changes from baseline over time in Leeds Sleep Evaluation Questionnaire (LSEQ), Greene Climacteric Scale (GCS), and Sheehan Disability Scale (SDS);
- the PD effect of 12-week administration of ESN364, in terms of changes over time in plasma concentrations of LH, FSH, E2, SHBG, leptin, insulin, C-peptide, and glycated hemoglobin (HbA1c);
- safety and tolerability of 12-week administration of ESN364, in terms of AEs, clinical laboratory tests, plasma bone density marker concentrations (bone alkaline phosphatase [BALP] and carboxy-terminal telopeptide of type I collagen [CTX]), vital signs, ECG, and physical examination.

Exploratory objectives are to:

- evaluate the effect of 12-week administration of ESN364 on body composition (lean mass, fat mass, bone mass/density) assessed by dual-energy X-ray absorptiometry (DEXA);
- assess ESN364 plasma concentrations from sparse PK sampling.

3. STUDY DESIGN

3.1 OVERVIEW OF STUDY DESIGN

This is a 12-week double-blind, placebo-controlled, parallel-group, multicenter, proof-of-concept study to assess the effect of 12-week administration of ESN364 in early postmenopausal women suffering from hot flashes.

[figure not shown]
A total of 80 subjects are planned to be included in the study, i.e., 40 subjects in the active treatment arm and 40 subjects in the placebo arm. Each subject will be administered an oral dose of 90 mg ESN364 b.i.d. or placebo b.i.d., as per pregenerated randomization list.

The study will consist of a screening period of maximum 4 weeks and a 12-week double-blind treatment period (Weeks 1-12), followed by a follow-up visit 2-3 weeks after the last study drug intake.

The study will be performed on an ambulatory basis. During the treatment period, subjects will be asked to come to the clinical site every 4 weeks (Day 1 and Weeks 4, 8, 12; Visits 2-5).

A schematic overview of the study design is shown in [Figure 5](#). The assessments performed are summarized per visit in the [Time and Events Schedule](#).

Figure 5: Schematic Overview of the Study

^a Screening is to be performed within 4 weeks prior to the first intake of study drug, with a minimum of 7 days to allow for baseline data collection of Hot Flash Score and Hot Flash Frequency.

An interim analysis on the primary endpoint, DEXA parameters and safety data will be performed once the first 16 subjects will have completed 12 weeks of treatment and the follow-up visit (or have discontinued earlier). The final analysis will be performed once all subjects will have completed 12 weeks of treatment and the follow-up visit (or have discontinued earlier).

3.2 DISCUSSION OF STUDY DESIGN

Dose Selection

LH secretion is a surrogate for the activity of the KNDy neuron. In the first-in-human Phase I study (see Section 1.3), the mid-range dose of ESN364, 60 mg/day, was demonstrated to be associated with a submaximal LH suppression, and thus a submaximal suppression of the KNDy neuron. ESN364 given as a dose of 180 mg/day was also tested in the first-in-human Phase I study and was demonstrated to be safe and well tolerated. LH suppression was maximal with this dose level. Hence, we expect that the 180-mg dose represents the dose associated with maximal suppression of the KNDy neuron.

During menopause, the negative feedback by E2 is unexisting, due to the cessation of estrogen production in the ovaries. The lacking negative estradiol feedback will cause the KNDy neuron to become hyperactive in an attempt to restore the needed estradiol levels via the increased release of LH/FSH. When dealing with an hyperactive state of the KNDy neuron, as assumedly is the case in the postmenopause period, a once-daily morning dose of ESN364 will probably not yield the desired suppression of KNDy at night, preventing night sweats. For this reason, a high dose of ESN364 (total daily dose of 180 mg) given as 90 mg b.i.d. will be tested to investigate the possibility to completely suppress LH secretion.

Placebo Control

Placebo control will be used to establish the frequency and magnitude of changes in clinical endpoints that may occur in the absence of active treatment.

Randomization and Blinding

Randomization will be used to avoid bias in the assignment of subjects to treatment, to increase the likelihood that known and unknown subject attributes (e.g., demographic and baseline characteristics) are evenly balanced across treatment arms, and to enhance the validity of statistical comparisons across treatment arms.

Blinded treatment will be used to reduce potential bias during data collection and evaluation of clinical endpoints.

4. SELECTION OF STUDY POPULATION

Screening for eligible subjects will be performed at a screening visit that is to be planned within 4 weeks prior to the first intake of study drug (with a minimum of 7 days to allow for baseline data collection of Hot Flash Score and Hot Flash Frequency).

In total 80 subjects are planned to be enrolled. Subjects will be randomized to one of 2 treatment arms in a 1:1 ratio: ESN364 90 mg b.i.d. (40 subjects) or placebo (40 subjects).

In- and exclusion criteria will be checked during screening (Visit 1) and reassessed prior to randomization (Visit 2).

Note: in case of an out-of-range clinical laboratory test, vital sign, or ECG value that will determine a subject's eligibility, or in case of a positive drug screen at screening, a retest can be done. Results of this retest must be available prior to randomization. The result of the retest will be considered for subject eligibility.

4.1 INCLUSION CRITERIA

Subjects meeting all of the following criteria are eligible to participate in this study:

1. Women, between 40 and 65 years old (extremes included) at screening;
2. Spontaneous amenorrhea for at least 12 consecutive months; or spontaneous amenorrhea for at least 6 months with biochemical criteria of menopause (FSH >40 IU/L); or spontaneous amenorrhea for at least 3 months with biochemical/physical criteria of menopause (FSH >40 IU/L and E2 <0.21 nmol/); or having had bilateral oophorectomy at least 6 weeks prior to screening (with or without hysterectomy);
3. At least 49 moderate or severe hot flashes or night sweats over a period of 7 consecutive days, as recorded in the daily diary during the screening period, with at least 4 of those days with 7 or more moderate or severe hot flashes per day;
4. In good general health as determined on the basis of medical history and general physical examination performed at screening; hematology and chemistry parameters, pulse rate and/or blood pressure, and ECG within the reference range for the population studied, or showing no clinically relevant deviations, as judged by the Investigator;
5. Negative urine test for selected drugs of abuse (amphetamines, tricyclic antidepressants, cannabinoids, cocaine, tetrahydrocannabinol, or opiates) at screening;
6. Negative serology panel (including hepatitis B surface antigen [HBsAg], anti-hepatitis C virus [HCV] and human immunodeficiency virus (HIV) antibody screens);
7. Negative urine pregnancy test at screening;
8. Informed Consent Form (ICF) signed voluntarily before any study-related procedure is performed, indicating that the subject understands the purpose of and procedures required for the study and is willing to participate in the study.

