Efficacy

Primary endpoint:

Changes from baseline in Hot Flash Score will be analyzed using an Analysis of Covariance (ANCOVA) model with treatment as fixed effect and baseline as covariate. If a significant difference between the treatment arms is present, differences between each active treatment arm and placebo will be tested, correcting for multiplicity.

Secondary endpoints:

Hot Flash Score and Hot Flash Frequency at all time points will be evaluated by means of descriptive statistics (actual values and changes from baseline) by treatment arm.

The percentage of subjects with at least 70% reduction from baseline in Hot Flash Score will be compared across the treatment arms, using chi-square or Fisher exact test, as appropriate.

The percentage of subjects with at least 50% reduction in the number of moderate and severe hot flashes will be compared across the treatment arms, using chi-square or Fisher exact test, as appropriate.

Questionnaires will be evaluated by means of descriptive statistics (actual values and changes from baseline) by treatment arm. HFRDIS, GCS, SDS and LSEQ total scores and subscores (if applicable) are to be reported.

Change in lean body mass, fat mass, and bone mass/density will be explored by means of descriptive statistics on the actual values, at each assessment time point and by treatment arm. Changes from baseline to Week 12 will be summarized by treatment arm.

Pharmacokinetics

Individual plasma ESN364 concentration values and actual sampling times relative to study drug intake will be listed. Descriptive statistics will be summarized by assessment time point.

Pharmacodynamics

Individual plasma hormone concentration values and actual sampling times relative to study drug intake will be listed. Descriptive statistics of the actual values and changes from baseline values will be summarized by assessment time point and by treatment arm.

Safety

Safety parameters will be tabulated and analyzed descriptively.

TIME AND EVENTS SCHEDULE

Assessments	Study Visit Time of Visit (Weeks) ^a	Visit 1: Screening ^b	Treatment Period				Visit 6: Follow-up ^c
			Visit 2 W1	Visit 3 W4	Visit 4 W8	Visit 5 W12	
Informed consent ^d		X					
In-/exclusion criteria		X	X				
Medical history/concomitant diseases		X					
Demographic data		X					
Physical examination ^e		X	X	X	X	X	X
Urine pregnancy test		X					
Urine drug screen		X					
Serology ^f		X					
Dual-energy X-ray absorptiometry ^g			X			X	

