Collection of hot flashes severity and frequency will be started on an ad hoc basis, but at a minimum twice-daily (morning and evening), via ePRO diary. Data on hot flash severity and frequency collected during the screening period will serve as baseline for Hot Flash Score and Hot Flash Frequency.

An overview of the assessments to be performed at the screening visit is provided in the [Time and Events Schedule](#).

Adverse events and concomitant therapies will be collected from signing of informed consent onwards (screening) through the follow-up visit.

All results from the screening procedure that are needed to evaluate eligibility, including the clinical laboratory results, must be available prior to randomization (Visit 2). Any abnormal assessment at the screening visit will be assessed according to its clinical relevance, and if found relevant, the subject will not be included in the study.

Unscheduled visits may be planned to assess, confirm, and follow-up on an out-of-range clinical laboratory test, vital sign, or ECG value that will determine a subject's eligibility, or in case of a positive urine drug screen. Results of this retest must be available prior to randomization. The result of the retest will be considered for subject eligibility. Findings made during unscheduled visits should be reported in the source documents and in the designated sections of the eCRF.

For screening failures, demographic data, the date of screening and signature of the ICF, and the reason(s) for screening failure will be recorded on the eCRF.

7.1.2 *Treatment Period (Visits 2-5; Weeks 1-12)*

Visit 2 should be scheduled in the morning between 7:00 and 10:00 AM, fasted. In- and exclusion criteria will be reassessed. Eligible subjects will be randomized in a 1:1 ratio to one of the 2 treatment arms (ESN364 90 mg b.i.d. or placebo). Predose assessments for efficacy (questionnaires), PK (ESN364 plasma concentrations), PD (hormone concentrations), and safety (clinical laboratory testing, bone density marker concentrations, vital signs, ECG, and physical examination) parameters will be made to serve as baseline (except for Hot Flash Score and Hot Flash Frequency, for which baseline will be data collected during the screening period).

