Blood samples for clinical laboratory tests will be taken at every visit and should be taken in a fasted state (overnight fast for at least 10 hours) for unbiased glucose, insulin, and C-peptide determination. Physical examination and vital sign assessments will also be made at every visit. An ECG will be recorded at every visit except Visit 4. Levels of the bone density markers BALP and CTX will be assessed at Visits 2 and 5 only.

DEXA will be repeated at Visit 5, before the last dose of the study drug. For practical reasons, the timing of DEXA may vary from the actual time of the visit, depending on the DEXA availability (DEXA appointment). The Visit 5 DEXA can be performed ± 4 days from the actual time of Visit 5. It is however to be performed before the last dose of the study drug; in case the DEXA appointment related to Visit 5 is scheduled later in time than Visit 5, study drug intake must be continued until DEXA has been performed (study drug intake at home and recorded in the ePRO diary).

Adverse events and concomitant therapies will be collected from signing of informed consent onwards (screening) through the follow-up visit.

Compliance towards study drug intake and ePRO completion will be checked at every visit during the treatment period. Compliance towards study drug intake will be assessed by counting returned dosage units in addition to ePRO entries. Any discrepancies between returned dosage units and dosing in the ePRO diary will be discussed with the subject for whom a discrepancy was seen.

An overview of the assessments to be performed during the treatment period is also provided in the [Time and Events Schedule](#).

7.1.3 *Follow-up Period (Visit 6)*

Two to 3 weeks after the last intake of the study drug, subjects will be asked to come to the clinical site for a follow-up visit.

An overview of the assessments to be performed at the follow-up visit is provided in the [Time and Events Schedule](#).

7.1.4 *Unscheduled Visits*

Unscheduled visits can be planned for instance:

- to obtain additional information to ensure safety to the subject. Additional blood and urine samples may be taken at the discretion of the Investigator.

- to collect an additional blood sample for PK assessment if a subject discontinues the study drug due to an AE;

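### The only pregnancy test is at screening, 7 to 28 days before first dose, which leaves a small, cheaply narrowed safety gap for women entering with 3 to <12 months' amenorrhea

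*Protocol*

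**What the plan says.** **The test.** Criterion 7 (Protocol, Section 4.1) requires a "Negative urine pregnancy test at screening". In the Time and Events Schedule, the row "Urine pregnancy test" has one mark, under Visit 1. Sections 7.1.1 and 7.5.1.2 also place the test at screening.

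**The interval.** Footnote b of the Schedule sets screening between 7 days and 4 weeks before first intake. Sections 4 and 7.1.2 have the eligibility criteria reassessed at Visit 2 before randomization. The retest note in Section 4 covers laboratory, vital-sign and ECG values and a positive drug screen. It does not mention the pregnancy test.

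**Who can enter.** Criterion 1 admits women from age 40. Besides 12 months' amenorrhea or bilateral oophorectomy, criterion 2 accepts "spontaneous amenorrhea for at least 6 months with biochemical criteria of menopause (FSH >40 IU/L") and "spontaneous amenorrhea for at least 3 months with biochemical/physical criteria of menopause (FSH >40 IU/L and E2 <0.21" nmol/L).

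**Related provisions.** Section 6.2 bars hormonal contraception and requires it to be stopped at least 6 weeks before screening. Non-hormonal methods are not barred. Criterion 3 requires at least 49 moderate or severe hot flashes or night sweats over 7 consecutive days, "as recorded in the daily diary during the screening period". On the diary, Section 7.1.1 says: "Collection of hot flashes severity and frequency will be started on an ad hoc basis, but at a minimum twice-daily". Section 1.5 describes the expected physiology as "anovulation with loss of P4 and E2 production, and consequently increase of LH/FSH". Under unscheduled visits, Section 7.1.4 states: "Additional blood and urine samples may be taken at the discretion of the Investigator".

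**The concern.** By requiring a negative pregnancy test at all, the protocol treats pregnancy as possible in at least some entrants. For that purpose the result that counts is the one at first dose, and no such result is obtained. The subgroup where this has any practical meaning is women without bilateral oophorectomy and with less than 12 months' amenorrhea. They are already amenorrheic, so a missed period gives no warning, and they may not use hormonal contraception.

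What is at stake is exposure of an undetected early pregnancy to up to 12 weeks of ESN364 at 180 mg/day. Section 1.5 says the compound lowers E2, LH and P4 in cycling women and that knowledge of its side effects is still limited. The point concerns patient safety only. It does not touch the primary endpoint, the ANCOVA, alpha or the planned 80 subjects.

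**Working it through.** **1. Check of the screening window.** The synopsis gives a maximum involvement of 19 weeks. Adding the maxima: 4 weeks' screening + 12 weeks' treatment + 3 weeks to follow-up = 19 weeks. The stated figure is reproduced, which confirms the 4-week limit.

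**2. Age of the pregnancy result.** At first dose it equals the interval from screening to first dose:
- minimum: 7 days
- maximum: 4 × 7 = 28 days

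With no repeat, it is up to 28 + 12 × 7 = 112 days old at the end of Week 12.

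**3. What a Visit 2 test would gain.** Let *g* be the interval from screening to Visit 2 (7 to 28 days) and *d* the number of days after conception before a urine test turns positive. The protocol does not give *d*, so I leave it open.
- Screening test only: conceptions in the last *g* + *d* days before first dose go undetected.
- Test added at Visit 2: only those in the last *d* days go undetected.
- Gain: (*g* + *d*) − *d* = *g*, that is 7 to 28 days, whatever *d* is.

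The remaining *d* days are not removed. With *g* = 7, a conception after screening is at most 7 days old at Visit 2 and would be found only if *d* were shorter than that. At short intervals the benefit is therefore mainly in pregnancies just missed at screening. Conceptions after screening become detectable when the interval is longer.

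**4. Other information available at Visit 2.**

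| Source | Timing | Does it replace a pregnancy test? |
|---|---|---|
| FSH and E2 for criterion 2 | Screening | No. They make pregnancy unlikely, but are as old as the pregnancy test |
| Visit 2 hormone samples | Visit 2, predose | No. They are baseline pharmacodynamic samples, frozen and shipped to the central laboratory (Sections 7.1.2, 7.3.1), not an eligibility check |
| Hot-flash diary | Screening through follow-up | No. It is current at Visit 2 but indirect |
| Extra sampling, Section 7.1.4 | Any time | Only if the investigator chooses |

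The 7-day diary run that qualifies a woman under criterion 3 can end between 7 − 7 = 0 and 28 − 7 = 21 days before first dose. That is the age of the qualifying run, not of the newest diary evidence, because recording continues up to Visit 2.

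**5. Event rate.** The protocol does not say what share of women will enter by the 3- or 6-month routes, so no expected number of pregnancies can be calculated.

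**The case against.** The strongest reply is that nothing here is wrong. All sections agree on a screening test. Criterion 7 is worded to be met at screening, so the Visit 2 reassessment is satisfied. The urine drug screen and serology are also done once, at Visit 1, and are equally old at first dose. A reader might infer that the Visit 2 recheck contradicts criterion 7 or cannot be carried out. The documents do not support that: the recheck can be carried out, but on an old result.

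The population definition also does much of the protective work. A pregnancy would have to coexist with FSH >40 IU/L (and low E2 on the 3-month route) and at least 49 qualifying episodes in a week, or ovulation would have to resume within 4 weeks. That stands, and it is why the risk is low. A reader might dismiss the diary as up to 21 days out of date, but recording runs to Visit 2, so that argument fails. What remains is that the diary is indirect evidence.

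A further objection is that the remedy is partial: it misses very recent conceptions and leaves the dosing period untested. This also stands. It limits what the change can be said to achieve, but does not cancel the gain of 7 to 28 days.

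Finally, the protocol identifies no embryo-fetal hazard, and fuller toxicology is in the Investigator's Brochure, which is not at hand. It would also be too strong to say that women receive no contraception instructions. No visible section requires a method, but the consent pages are not shown.

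**Conclusion.** The point holds as a minor safety improvement, optional for the sponsor. The pregnancy result is 7 to 28 days old at first dose. In women without bilateral oophorectomy and with 3 to <12 months' amenorrhea, neither the retest note nor the optional sampling ensures a newer one. The probability of harm is expected to be low but cannot be quantified from the protocol.

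This rests on two assumptions: that pregnancy remains possible in this subgroup, which the protocol accepts by testing for it, and that the removed consent pages do not add a predose test. The case for acting is that a rare but serious and avoidable exposure can be made less likely at almost no cost.

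**What to change.** Amend criterion 7 (in the synopsis and Section 4.1), the Time and Events Schedule and Section 7.1.2, with a matching line in Section 7.5.1.2. Add a urine pregnancy test at Visit 2, predose and before randomization, for women without bilateral oophorectomy and with less than 12 months' amenorrhea. Require a negative result to randomize. Use the urine already collected at Visit 2 for on-site dipstick urinalysis, taken early enough for the result to be read before randomization.

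For these women the result would then be 0 days old at first dose instead of 7 to 28.

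**Cost:** at most one extra urine test per woman in the subgroup, so no more than 80 × 1 = 80 among the planned subjects and in practice fewer, plus a small amendment. There is no extra visit or invasive procedure, and no change to sample size or analysis.

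**Limits:** conceptions in the last days before Visit 2 would still be missed, and the 12 weeks of dosing remain without a test.
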